6.1.2. RSV

Geometric means and positivity status for RSV viral loads will be derived according to the following table:

Component	Raw result	Derivation for GM calculation	Derivation for positivity status
RSV-A	<llod< td="">LLOD /2	NEG	</llod<>	LLOD /2	NEG
	≥ LLOD	Exact value	POS
RSV-B	< LLOD	LLOD /2	NEG
	≥ LLOD	Exact value	POS

Table 5Derivation rule for GMT calculation of RSV viral load

The thresholds used for the derivation are detailed in the following table:

Table 6 Derivation rule for positivity status of RSV viral load

Component	Method	Unit	LOD
RSV-A	RT-qPCR	copies of RSV RNA per mL	1123
RSV-B	RT-qPCR	copies of RSV RNA per mL	1467

The subject will be considered to be RSV positive when the RSV infection will be confirmed on nasal swab by quantitative polymerase chain reaction (PCR) using both RSV-A (fields [LABO_RES.COMPONEN] = "RSV-A" and [LABO_RES.METHOD] = "QRTPCR" and [LABO_RES.RAWRES]) and RSV-B (field [LABO_RES.COMPONEN] = "RSV-B" and [LABO_RES.METHOD] = "QRTPCR" and [LABO_RES.RAWRES]) tests.

The subject will be considered as positive if one or both tests are positive.

A RSV-A test will be considered:

- Positive if [LABO_RES.RAWRES] \geq 1123 copies/ml
- Negative if [LABO_RES.RAWRES] < 1123 copies/ml

A RSV-B test will be considered

- Positive if $[LABO_RES.RAWRES] \ge 1467$ copies/ml
- Negative if [LABO_RES.RAWRES] < 1467 copies/ml

Please note that the RSV01 test will not be considered to derive RSV status for primary objectives.

6.1.3. RSV neutralising antibody

Geometric means for RSV neutralising antibodies will be derived according to the following table:

Table 7Derivation rule for GMT calculation of RSV neutralizing Antibody

Assay	Raw result	Derivation for GMT calculation
RSV-A neutralising Antibody	<8	4
	≥8	Exact value
RSV-B neutralising Antibody	<6	3
	≥6	Exact value

Seropositivity status for RSV neutralising antibodies in cord blood samples will be derived according to the following table:

Table 8Derivation rule for seropositivity status of RSV neutralizing Antibody
in cord blood samples

Assay	Raw result	Derivation for seropositivity status
RSV-A neutralising Antibody in cord blood	< 8	NEG
	≥8	POS
RSV-B neutralising Antibody in cord blood	< 6	NEG
	≥6	POS

Seropositivity status for RSV neutralising antibodies in blood samples will be derived according to the following table:

Table 9Derivation rule for prevalence of infection of RSV neutralizing
Antibody in blood samples

Assay	Raw result	Derivation for infection status
RSV-A neutralising Antibody in blood sample	< 2 fold of expected value*	Non infected
month 2, 4, 6, and 12	≥ 2 fold expected value	Infected
RSV-A neutralising Antibody in blood sample	< 8	Non infected
month 18 and 24	≥ 8	infected
RSV-B neutralising Antibody in blood sample month 2, 4, 6, and 12	< expected value	Non infected
	≥ expected value	Infected
RSV-B neutralising Antibody in blood sample month 18 and 24	< 6	Non infected
	≥ 6	infected

*Expected value is calculated using Natural decay model.

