RSV infections result in high rates of hospitalization in infants, a large disease burden among infants and young children, and excess mortality in the elderly [Graham, 2011]. RSV infects 50-70% of infants during the first year of life and essentially all children will have had an RSV infection by their third birthday [Hall, 2004]. In the early months of life, infants may have protection against RSV through the maternal antibodies transferred to them during pregnancy. High titers of maternally derived RSV-neutralizing antibodies [Roca, 2002] have been shown to be inversely associated with the incidence of RSV associated-acute LRTI during the first 6 months of life, whereas incomplete transfer of maternally derived RSV-neutralizing antibodies has been implicated in the increased risk of severe RSV infection in preterm infants [de Sierra, 1993]. Previous infection with RSV does not prevent subsequent infections. Therefore, re-infection with RSV occurs throughout an individual's lifetime and is common in all age groups [Simoes, 1999; Krilov, 2011].

Globally, it is estimated that in children below 5 years of age, RSV causes >30 million acute lower respiratory infections (LRTI) each year resulting in more than 3 million hospitalizations, making it the most common cause of hospitalization for LRTI or all cause from any single pathogen in this age group [Nair, 2010]. RSV is the most common cause of bronchiolitis and pneumonia in children less than 1 year of age worldwide, with

highest risk in children less than 6 months of age [Nair, 2010; Langley, 2011]. A United States (US) based study conducted in children less than 18 years of age, found RSV in 58% of the hospitalizations for LRTI compared to parainfluenza virus 1-3 in 17%, influenza A/B in 21%, adenovirus in 2% and rhinovirus in 2% [Henrickson, 2004]. On a community level, a US day-care based study assessing the causes of respiratory tract infection (RTI) in children less than 1 year of age found that RSV infection was present in 11% of the cases, compared to rhinovirus in 35%, adenovirus in 22%, human coronavirus in 15%, parainfluenzavirus in 12%, human meta-pneumovirus in 4% and influenza A in 2% [Fairchok, 2010]. This difference between community and hospital proportions of RSV related infections indicates the propensity of RSV to cause more serious cases of RTI, mainly LRTI, compared to other viruses.

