9.7.2. Secondary objectives

• To determine the total health burden of non-RSV-associated RTI with a suspicion of involvement of the lower respiratory tract.

Incidence rates will be calculated as the number of non-RSV-associated RTI with a suspicion of involvement of the lower respiratory tract over the number of children-years observations, overall and by subgroups.

Descriptive statistics of the different types of healthcare utilization will be provided (proportions, duration, etc.) among non-RSV-associated RTI with a suspicion of involvement of the lower respiratory tract, overall and by subgroups.

• To evaluate the association between RSV-associated LRTI, RSV-associated severe LRTI and RSV neutralizing antibodies in the baseline cord blood samples collected from subjects, at birth.

The impact of the level of RSV neutralizing antibodies in the baseline cord blood samples on the risk of having a RSV-associated LRTI and RSV-associated severe LRTI will be assessed through a statistical model.

Incidence rates will be calculated overall and by level of antibodies in the cord blood sample, as the number RSV-associated LRTI/severe LRTI as classified by the case definition and severity scale over the number of children-years observations.

• To determine the prevalence of RSV infection, at 2, 4, 6, 12, 18 and 24 months in a randomly selected sub-cohort of subjects by assessing antibodies in serum.

The primary analysis will be based on ATP sub-cohort for this objective.

Infection by RSV will be assessed (with 95% CI) by time point as the proportion of samples with a positive score of antibody titer after adjusting for baseline antibody results over the total number of samples.

Scores will be determined based on the measured antibody titer *vs*. the expected antibody level at the time of sampling based on the individual baseline (cord blood) value and the average, modelled decay rate.

• To assess the between calendar year variability in the incidence rates of RSVassociated LRTI.

Incidences rates will be calculated as the number of RSV-associated LRTI/severe LRTI as classified by the case definition and severity scale, over the number of children-years observations, in the subgroups of subjects recruited from months 1-6 and from months 13-18.

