2. STUDY DESIGN

2.1. Design summary

In the primary study, subjects were to be followed-up from birth up to the age of 2 years for RSV LRTI. Episodes of wheeze and diagnoses of asthma were also documented.

Figure 1 Study design diagram for the primary study (from birth up to the age of 2 years for detection of RSV LRTI)

V = Visit; D = Day; M = Month

ICF = Informed Consent Form; CBS = Cord Blood Sample; NS = Nasal Swab; DC = Diary Card; BS = Blood Sample ¹ An examination visit (off-site/site) is to occur for new or worsened, potential LRTI case as identified during active or passive follow-up contact. The examination visit needs to occur as soon as possible and no later than 72 hours after the potential LRTI was identified during a follow-up contact. Each subject may have none, single or multiple examination visits over the course of the study.

² A sub-cohort of subjects will be randomized for a single blood draw to occur at one of the six possible time points and will have a Visit 3 corresponding to this time point (if still participating at that time); either V3a at 2, V3b at 4, V3c at 6, V3d at 12, V3e at 18 or V3f at 24 months.

* All follow up procedures associated with V2 (e.g. ICF) must be performed within 5 working days after birth.

200150 (EPI-RSV-005 BOD)

Statistical Analysis Plan Amendment 1 Final

- Type of design: Prospective, epidemiological, interventional, multi-country, cohort study.
- Study population:
 - A cohort of approximately 2400 infants will be included in the study at birth and followed-up up to 2 years of age.
 - A sub-cohort of subject will be randomized for a single blood draw to one of the time point at 2, 4, 6, 12, 18 or 24 months of age as described in Table 1.

Table 1Blood sample collection

Time point	Seroprevalence sub-cohort Number of allocated subjects*
2 months	200
4 months	200
6 months	250
12 months	300
18 months	450
24 months	600
Total	2000

Note: Only one blood sample will be withdrawn from each subject in this sub-cohort.

*Number of subjects selected per time point is calculated based on the required number of subjects for adequate analysis considering an accumulating drop-out of subjects. Actual numbers might be less due to drop-outs and exclusion of subjects with gestational age <36 weeks..

- Type of study: Self-contained.
- Data collection: Electronic case report form (eCRF).
- Biological samples (Primary Study only):
 - Cord Blood collected from all participating subjects, at birth.

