Descriptive analyses (seropositivity rate with 95% CIs, geometric mean, median, min, max) of RSV neutralizing antibodies at 2, 4, 6, 12, 18 and 24 months will be presented.

Prevalence of infection will be determined at the time of the analysis based on the measured antibody titer *vs*. the expected antibody level at the time of sampling based on the individual baseline (cord blood) value and the average, modelled decay rate for subjects with blood sampling at time point 2, 4, 6, and 12 month. RSV infection is defined as titers 2-fold higher than expected value. For subjects with blood sampling during second year of life, a sample with positive result will count as prevalence of infection.

All exact 95% CI will be two-sided, based on the Clopper-Pearson based on a mathematical relationship (see Fleiss et al (2003), p. 25) between the F distribution and the cumulative binomial distribution.

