6.9.3. Analysis of tertiary objective: natural decay of maternal neutralizing antibodies

The analysis will be based on total sub-cohort subject with blood sampling at month 2, 4, 6, and 12 for this objective.

The decay of maternal antibody levels over time will be analysed graphically and by a linear regression of the log of maternal antibody levels. A true, natural decay curve will be explored by stochastically reducing the sample to uninfected subjects only. The following steps will be taken to identify, confirmed and suspected infected subjects to eliminate these from the sample;

STEP 1: Subjects with an RSV positive *nasal swab* during the study before time of sampling will be eliminated. Note that such subjects are removed from the analysis because they are infected by RSV; as a consequence their antibody levels are no longer maternal antibody levels.

STEP 2: Run the model and compute expected value based on the decay curve for each subjects

200150 (EPI-RSV-005 BOD)

Statistical Analysis Plan Amendment 1 Final

STEP 3: Subjects with an antibody titer at the sampling time that is more than 2-fold above the expected value based on their baseline (cord blood) value and the established decay curve will be considered to have been infected, eliminated and the decay curve refined.

STEP 4: Step 3 is repeated up to 5 times until the most accurate decay curve is established.

The natural decay of antibody will be determined using linear regression between the log of antibody level (Y) and time t (age in months) with subject as a random effect. Indeed, all subjects have RSV neutralizing antibodies measured at birth (cord blood). And, each subject of the Total sub-cohort will be randomly selected to be sampled for RSV neutralizing antibodies at one of the following time points: 2, 4, 6, and 12 months. For the natural decay model, subjects will have maximum 2 RSV neutralizing antibodies measures, one at birth and one either at 2 months or 4 or 6 or 12 months.

A table will describe the decay rate and half-life statistics of the natural decay model.

A descriptive table will describe the serology status (positive/negative) according to the natural decay analysis.

A sensitivity analysis of the decay curve will be explored in sub-sample consisting of the subjects born 'off-season' as these have the lowest likelihood of having been infected.

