Each step/model is used to reduce the sample to uninfected subjects only. Subjects with an antibody titer at the sampling time that is more than 2-fold above the expected value based on their baseline (cord blood) value and the established decay curve will be considered to have been infected, eliminated and the decay curve refined. The expected value of antibody titer of each subject is computed using based on their baseline (cord blood) value and the established decay curve defined using the natural decay rate at the previous step.

The decay model is fitted only using subject with blood sample at 2, 4, 6, and 12 month

The sequential analysis is repeated up to 5 times until the most accurate decay curve is established

N = Number of subjects used in the model

LL, UL for percentage = Lower and Upper confidence limits

Template 51 Decay rate of [RSV-A – RSV-B] maternal antibody levels assuming a fixed rate of decay Neutralizing antibodies per months) (PPS subcohort)

q1-q4: quartile of [RSV-A - RSV-B] cord blood antibodies

200150 (EPI-RSV-005 BOD)

Statistical Analysis Plan Amendment 1 Final

Template 52 Prevalence of [RSV A – RSV B – RSV] infection, at 2, 4, 6, 12, 18 and 24 months in a randomly selected sub-cohort of subjects by assessing antibodies in serum [Overall – by country] (PPS subcohort)

					95% CI	
Country	Time point (Month)	Ν	n	Proportion (in %)	LL	UL
[Overall – by country]	2					
	4					
	6					
	12					
	18					
	24					

N = total number of subject at time of sampling

n = number of subjects with an antibody titer at the sampling time that is more than 2-fold above the expected value for month 2, 4, 6, and 12 month subject, and number of subject with antibodies in serum above [8 – 6] for month 18 and 24 subjects

LL, UL for percentage = Exact 95% Lower and Upper confidence limits

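### SAP Table 9 calls a child RSV-B infected at the expected titre itself for months 2 to 12, while every other rule in the SAP uses 2-fold; about half of uninfected children or more would be misclassified.

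*SAP*

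**What the plan says.** Table 9 in SAP 6.1.3 is the derivation rule for infection status in the follow-up blood samples. For months 2, 4, 6 and 12 it takes the expected titre from the natural decay model. RSV-A is infected at "≥ 2 fold expected value"; RSV-B is infected at "≥ expected value" and non-infected below it. At months 18 and 24 both subtypes use the assay cut-offs (8 and 6).

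Two other places define the same endpoint:

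- SAP 6.9.2, without separating the subtypes: "RSV infection is defined as titers 2-fold higher than expected value".
- The footnote of Template 52, whose title covers RSV A, RSV B and RSV: "more than 2-fold above the expected value for month 2, 4, 6, and 12 month subject".

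The model that supplies the expected value also uses 2-fold. Step 3 of SAP 6.9.3 removes as infected those children whose titre is "more than 2-fold above the expected value based on their baseline (cord blood) value"; protocol 9.7.3 has the same step. Protocol 9.7.2 compares the measured titre with "the expected antibody level at the time of sampling based on the individual baseline (cord blood) value and the average, modelled decay rate" and gives no fold, so it does not settle the matter. SAP section 9, which lists changes from the planned analyses, mentions no RSV-B exception.

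**The concern.** Two programmers working from different sections of the same SAP would produce different RSV-B prevalences from the same samples at four of the six time points. If the combined RSV version of Template 52 counts a child positive on either subtype, it would be affected too.

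The Table 9 rule is also at odds with the model it depends on. A child at 1 to 2 times the expected titre is kept as uninfected when the curve is fitted, and is then counted as RSV-B infected against that curve. Because the expected value is the centre of the fit, a cut-off placed there cannot separate infected from uninfected children: an uninfected child is about equally likely to fall on either side.

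**Working it through.** The plan states no misclassification rate, so there is no figure of its own to reproduce. The check has two parts: the text, and the size of the error.

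**Text, months 2 to 12**

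| Place | RSV-A | RSV-B |
|---|---|---|
| SAP 6.1.3, Table 9 | 2-fold | 1-fold |
| SAP 6.9.2 | 2-fold | 2-fold |
| SAP Template 52 footnote | more than 2-fold | more than 2-fold |
| SAP 6.9.3 Step 3; protocol 9.7.3 (model trimming) | more than 2-fold | more than 2-fold |

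**Inputs for the size**

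- Allocated samples at months 2, 4, 6 and 12 (SAP 2.1, Table 1): 200 + 200 + 250 + 300 = 950. The SAP notes "Actual numbers might be less due to drop-outs".
- Residual SD of log10 titre in uninfected children: not in the documents. Assumed 0.15, 0.3 and 0.5.
- True prevalence p: assumed 10% to 70%. Protocol 1.1.1 says "RSV infects 50-70% of infants during the first year of life", for any RSV and with no A/B split.

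**Step 1. Uninfected children called infected, before trimming.** With symmetric log residuals the 1-fold rule gives P(residual ≥ 0) = 0.5 at any SD. With normal residuals the 2-fold rule gives 1 − Φ(0.301/SD), where 0.301 = log10 2.

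| SD (log10) | 1-fold | 2-fold | Between 1 and 2 times expected |
|---|---|---|---|
| 0.15 | 50% | 2% | 48% |
| 0.3 | 50% | 16% | 34% |
| 0.5 | 50% | 27% | 23% |

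The last column is the group treated as uninfected by the model and as infected by Table 9.

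**Step 2. With the SAP's trimming.** Removing only high titres pulls the fitted curve down. A simulation used 950 uninfected children, regressed the change from cord titre on age, and removed children more than 2-fold above expected in up to 5 rounds (400 replicates):

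| SD (log10) | 1-fold | 2-fold | Gap (points) |
|---|---|---|---|
| 0.15 | 51.9% | 2.5% | 49 |
| 0.3 | 64.8% | 27.2% | 38 |
| 0.5 | 79.2% | 61.1% | 18 |

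This is a simplified fit, not the SAP's random-effect model. A second simulation added infected children, assumed half-lives of 1.0, 1.5 and 2.5 months, and was run with and without setting RSV-B titres below 6 to 3. Over SDs of 0.5 to 1.5 log2 (about 0.15 to 0.45 log10), 51% to 82% of uninfected children were called infected at 1-fold. Single time points fell as low as 44% in some runs with the floor.

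**Step 3. Apparent RSV-B prevalence, before trimming.** Apparent prevalence = p + (1 − p) × false-positive share, with full sensitivity under both rules.

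| True p | 1-fold | 2-fold |
|---|---|---|
| 10% | 55% | 12–35% |
| 30% | 65% | 32–49% |
| 50% | 75% | 51–64% |
| 70% | 85% | 71–78% |

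**Step 4. Extra false RSV-B positives among the 950.** Count = 950 × (1 − p) × gap. The untrimmed gaps run from 0.226 to 0.478, the trimmed gaps from 0.181 to 0.494.

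| True p | Untrimmed | Trimmed |
|---|---|---|
| 10% | 194–408 | 155–422 |
| 50% | 108–227 | 86–235 |
| 70% | 65–136 | 52–141 |

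**The case against.** The strongest reply is that this is a drafting slip. The RSV-A rows of the same table, the section for this objective and the output shell all say 2-fold, and a programmer might well follow those. That is plausible, but Table 9 is the stated derivation rule and following it would be a reasonable reading. If 1-fold was intended, the other sections are wrong, so a correction is due either way.

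A second reply is that one half is conditional. It needs symmetric residuals and a curve centred on uninfected children; trimming and the assay floor disturb both, and SAP 6.9.3 itself allows the decay analysis to be adapted for samples below the quantification limit. This stands, but in the simulations the overall 1-fold share stayed above one half.

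A third is that the 2-fold rule is itself poor when the residual SD is large: 61% in the trimmed simulation at 0.5 log10, and up to 34% even at about 0.15 log10 with the floor and the shortest half-life. This also stands. The point here is the inconsistency and the added error, not that 2-fold is accurate. Setting sensitivity to 1 for both rules also hides any gain in sensitivity at 1-fold, though the SAP makes no such argument.

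Loss of the words in text extraction is unlikely, since they are missing from both RSV-B cells and present in both RSV-A cells. The original page is still worth a look.

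**Conclusion.** The concern holds. The contradiction is certain from the text and needs no modelling. As written, Table 9 would call roughly half or more of uninfected children RSV-B infected at months 2 to 12. The excess over the 2-fold rule is 23 to 48 points before trimming and 18 to 49 points after it, for assumed SDs of 0.15 to 0.5 log10. The effect on reported prevalence shrinks as true prevalence rises: before trimming, from 20–43 points at 10% to 7–14 points at 70%.

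These sizes rest on the assumed SD range, symmetric residuals (normal for the 2-fold rule), full sensitivity, one prevalence across the four time points, and all 950 allocated samples being available.

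The weight is moderate. The objective is secondary and the analysis descriptive (SAP section 7). RSV-A, months 18 and 24, and the co-primary incidence analyses, which use RT-qPCR, are untouched. It should be fixed before the prevalence tables are programmed.

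**What to change.** In Table 9, change the two RSV-B cells for months 2, 4, 6 and 12 to the 2-fold rule used for RSV-A: non-infected below 2 times expected, infected at or above it. At the same time choose one boundary, since Table 9 includes exactly 2-fold while Template 52 and SAP 6.9.3 require more than 2-fold.

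If a 1-fold RSV-B rule is intended, give the reason, amend SAP 6.9.2 and the Template 52 footnote, and explain how it fits with the 2-fold trimming in SAP 6.9.3.

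The cost is two table cells and a wording alignment, with no new data. Reported RSV-B prevalence at months 2 to 12 will be lower than under Table 9 as it stands.

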6.1.4. Cox model

6.1.4.1. Gestational age at birth

The gestational age at birth will be categorized as followed:

- Less or equal to 36 weeks
- More than 36 weeks

6.1.4.2. Birth weight

The birth weight will be categorized as followed:

- Less than 2.5 kg
- More or equal to 2.5 kg

6.1.4.3. Apgar at 5 mins of age

The Apgar at 5 mins of age will be categorized as followed:

- 0-3 inclusive,
- 4–6 inclusive,
- 7 or greater

6.1.4.4. Family history of respiratory disease

The subject will be considered to have family history of respiratory disease if at least one of its first degree relative (i.e. mother father or sibling) has respiratory disease.

